#### **6.2.4 Definitions of dose-limiting toxicities (DLTs)**

A dose-limiting toxicity (DLT) is defined as an adverse event or abnormal laboratory value of CTCAE grade  $\geq 3$  assessed as having a suspected relationship to study drug, and unrelated to disease, disease progression, inter-current illness, or concomitant medications that occurs within the first cycle of treatment with single agent LAG525 or within the first two cycles of treatment with the combination of LAG525 and PDR001, and meets any of the criteria included in [Table 6-4](#).

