### 6.2.3 Guidelines for dose escalation and determination of MTD/ RP2D

The maximum tolerated dose (MTD) is defined as:

- Arm A and Arm C (single-agent LAG525): for patients enrolled in the single agent arm with administration of single agent LAG525, the highest drug dosage that is unlikely (< 25% posterior probability) to cause DLT in 33% or more of the treated patients in the first cycle of study treatment under that schedule. The DLT window for **Arm A and C is one cycle (28 days, 21 days for patients on Q3W dosing schedule)**. Patients enrolled in this arm must receive at least two doses (Q2W schedule) of LAG525 to be considered evaluable for toxicity. For the Q3W and Q4W schedule, one dose must be received.
- Arm B (combination of LAG525 and PDR001): for patients enrolled in the combination treatment arm in the dose escalation part with administration of both LAG525 and PDR001, the highest combination drug doses that is unlikely (< 25% posterior probability) to cause DLT in 33% or more of the treated patients in the first two cycles of study treatment under that schedule. The DLT window for **Arm B is two cycles (56 days, 42 days for patients on Q3W dosing schedule)**. Patients must receive at least three doses (Q2W schedule) of both study drugs during the first two cycles (DLT observation window) to be considered evaluable for toxicity. For the Q3W and Q4W schedule, patients must receive 2 doses of both study drugs during the first two cycles.

During the dose escalation of combination agents, only 1 of the 2 study drugs can be escalated at a time.

Adverse events and laboratory abnormalities considered to be DLTs are defined in [Table 6-4](#).

For Arm B, since several combinations may correspond to this definition, more than one MTD may be identified with different doses of the study drugs. One (or more) of these MTDs or a suitable lower dose combination will then be selected as the RP2D(s).

The applied adaptive Bayesian methodology provides an estimate of the single-agent LAG525 and the combinations of LAG525 and PDR001 not exceeding the MTD. Typically the MTD is a tested dose (or combination) with maximum probability of targeted toxicity (DLT rate between 16% and <33%). The use of the EWOC principle limits the risk that a potential next dose will exceed the MTD [Section 10.4.2](#).

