### **6.2.3.1 Implementation of Dose Escalation Decisions**

To implement dose escalation decisions, the available toxicity information (including all safety data, AEs Grade  $\geq 2$  and laboratory abnormalities that are not DLTs), the assessment of those doses satisfying the EWOC criterion from the BLRM, and the available PK [REDACTED] information will all be evaluated by the Investigators and Novartis study personnel (including the study physician and statistician) during a dose decision meeting by teleconference. All occurrences of DLT will be discussed and agreed at the dose decision teleconference among participating investigators and Novartis study personnel.

Cohort enrollment and drug administration at the next higher dose level may not proceed until the investigator receives written confirmation from Novartis indicating that the results of the previous dose level were evaluated and that it is permissible to proceed to a higher dose level with written confirmation of the next higher dose level to be tested.

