##### **DLT window:**

- Arm A and Arm C with single agent LAG525: 28 days (one cycle) (21 days for patients on Q3W dosing schedule).
- Arm B with combination of LAG525 and PDR001: 56 days (two cycles) (42 days for patients on Q3W dosing schedule).

Emerging data from the new field of immune-immune combination studies suggest that some immune-related adverse events have a prolonged latency ([Wolchok 2013](#)). As such, the DLT window for the combination arm in this trial is extended to the length of two cycles or 56 days.

National Cancer Institute Common Terminology Criteria for Adverse events (NCI CTCAE) version 4.03 will be used for all grading unless otherwise specified. For the purpose of dose-escalation decisions, DLTs will be considered and included in the BLRM.

The investigator must notify the Sponsor immediately of any unexpected CTCAE grade  $\geq 3$  adverse events or laboratory abnormalities. Prior to enrolling patients into a higher dose level, CTCAE grade  $\geq 2$  adverse events will be reviewed for all patients at the current dose level.

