**The following Grade 2 AEs related to study treatment are considered DLTs:**

Ocular disorders	Grade 2 eye pain or reduction of visual acuity are DLTs if they do not respond to topical therapy and do not improve to Grade 1 severity within 2 weeks of the initiation of topical therapy, OR if they require systemic treatment.
Pneumonitis	Grade 2 pneumonitis is a DLT if it does not resolve to $\leq$ Grade 1 within 7 days of starting corticosteroids.
Myocarditis	Grade 2 myocarditis is a DLT.
Colitis	Grade 2 colitis is a DLT if it persists $>$ 7 days despite treatment with corticosteroids.
Hepatic	Grade 2 ALT or AST accompanied by bilirubin $>1.5$ x ULN is a DLT.
Dermatologic	Grade 2 bullous disease that does not resolve to $\leq$ Grade 1 within 7 days of starting corticosteroids is a DLT.
Other adverse events	Other clinically significant toxicities, including a single event or multiple occurrences of the same event that lead to a dosing delay of $>$ 7 days within the DLT window, may be considered to be DLTs by the Investigators and Novartis, even if not CTCAE grade 3 or higher. Infusion reactions will not be considered as dose limiting because they are idiosyncratic and not related to dose.

\* Depending on the nature of the AE, there may be cases where immune-related Grade 2-3 AEs of any duration warrant declaration of a DLT and permanent study discontinuation (e.g. Stevens-Johnson Syndrome (SJS)). DLT determination not already outlined in this table will be made on a case-by-case basis after Investigator discussion with the Novartis Medical Monitor.

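### The lead-in to protocol Section 6.2.4 restricts DLTs to CTCAE grade ≥3, contradicting the Grade 2 rows of Table 6-4, which Section 6.2.3 names as the definition

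*Protocol*

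**What the plan says.** The lead-in of protocol Section 6.2.4 sets several conditions jointly. The first is severity: "A dose-limiting toxicity (DLT) is defined as an adverse event or abnormal laboratory value of CTCAE grade" ≥3. The event must also be suspected to be related to study drug, be "unrelated to disease, disease progression, inter-current illness, or concomitant medications", fall inside the DLT window, "and meets any of the criteria included in" Table 6-4.

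Table 6-4 has two blocks. The first makes related Grade 3 or 4 events DLTs, apart from listed exceptions. The second is headed "The following Grade 2 AEs related to study treatment are considered DLTs". It covers ocular, pneumonitis, myocarditis, colitis, hepatic and bullous skin events, some with conditions on duration or response to treatment. Its last row lets the investigators and sponsor declare other clinically significant toxicities to be DLTs "even if not CTCAE grade 3 or higher", and says that infusion reactions are not dose limiting.

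Section 6.2.3 states which text defines the endpoint: "Adverse events and laboratory abnormalities considered to be DLTs are defined in" Table 6-4. The SAP (Sections 2.2 and 2.6.1) uses the term DLT without defining it, so it does not settle the matter.

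**The concern.** The lead-in joins its conditions with *and*, so no Grade 2 event can meet it, yet Table 6-4 calls some Grade 2 events DLTs. One of the two texts must be wrong.

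This matters because DLT incidence is the Phase I primary variable (protocol Section 10.4.1) and the input to the Bayesian logistic regression model (BLRM). A DLT is also one of two routes into the DDS (protocol Section 10.1.4). Read literally, the lead-in could do two things:

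- **Undercount.** A patient with a listed Grade 2 event is counted as evaluable without a DLT.
- **Exclude.** Table 6-5 requires discontinuation for Grade 2 myocarditis and for Grade 2 transaminitis with bilirubin above 1.5 × ULN (Gilbert's syndrome excepted). A patient stopped for one of these before minimum exposure enters the DDS only if the event is a DLT. Minimum exposure is two doses in Arms A and C on Q2W. In Arm B it is three doses of each drug on Q2W, or two on Q3W and Q4W. On single-agent Q3W or Q4W one dose is enough, so the effect there would usually be an undercount.

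**Working it through.** **Which text governs.** Section 6.2.3 names Table 6-4 as the definition, and applying the lead-in literally would void a whole block of that table. There is no explicit precedence clause, but this points to the grade ≥3 floor as the error.

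**Which versions applied to Phase I.** Amendment 09 (16-Aug-2018) revised both Table 6-4 and Table 6-5. From the amendment study-status sections:

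- 31-May-2017: 254 treated, all in Phase I, 133 of them single agent, so 254 − 133 = 121 combination.
- 21-Jun-2018: 255 treated in Phase I. Amendment 10 gives the split as 134 + 121 = 255.

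All 121 combination patients were therefore treated by 31-May-2017, and their 56-day windows ended by late July 2017. The one later patient was single agent and treated by 21-Jun-2018, so that 28-day window ended by about 19-Jul-2018. Every window closed before Amendment 09.

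**Sensitivity of the model to one DLT (Arm A).** Inputs from the protocol:

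- Model (Section 10.4.2): logit π(d) = log α + β log(d/3).
- Prior for (log α, log β) (Table 14-7): weight 0.8 on means (−2.692, −1.26) with SDs (1, 1); weight 0.2 on means (−2.3, 0) with SDs (2, 1); zero correlation.
- Posterior ∝ prior × Π π(d)^r (1 − π(d))^(n−r), with r DLTs in n patients at each dose.
- P(over) = posterior probability that π(d) ≥ 0.33. A dose is barred at 0.25 or more.

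Reproducing the plan's own figures:

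| Table 14-11 scenario | Data (DLTs/patients) | Dose | P(over) printed | Computed |
|---|---|---|---|---|
| 4 | 0/4 at 1, 0/3 at 3 mg/kg | 10 | 0.108 | 0.108 |
| 5 | 0/4 at 1, 1/3 at 3 mg/kg | 3 | 0.055 | 0.055 |
| 7 | 0/4 at 1, 0/6 at 3 mg/kg | 10 | 0.084 | 0.088 |
| 8 | 0/4 at 1, 1/6 at 3 mg/kg | 10 | 0.193 | 0.185 |

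*Early cohort.* Scenario 5 differs from scenario 4 by one DLT at 3 mg/kg. Table 14-11 does not print P(over) at 10 mg/kg for scenario 5; the reconstruction gives 0.262. Missing that DLT turns 0.262 (10 mg/kg barred) into 0.108 (allowed). Dropping the patient instead (0/2 at 3 mg/kg) gives 0.118, also allowed. One DLT need not matter: scenarios 7 and 8 have the same next dose.

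*Accumulated data.* Table 14-22 Q2W rows (cut-off 22 January 2016): 1/12, 0/11, 2/4 and 0/4 at 1, 3, 5 and 10 mg/kg, so 12 + 11 + 4 + 4 = 31 patients. The Q4W rows are left out because the protocol down-weights other schedules. P(over) at 10 mg/kg is 0.032. With one DLT added:

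| Dose of added DLT | Evaluable patient reclassified | Dropped patient restored |
|---|---|---|
| 1 mg/kg | 0.034 | 0.033 |
| 3 mg/kg | 0.061 | 0.056 |
| 5 mg/kg | 0.083 | 0.071 |
| 10 mg/kg | 0.130 | 0.093 |

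All are below 0.25. Two patients reclassified at 10 mg/kg (2/4) would cross it, at 0.372; two restored there (2/6) would not, at 0.208.

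**Arm B.** Final counts are not in the documents, so this is an assumption: 0/4 at 1/1 and 0/5 at 1/3 mg/kg, plus the Table 14-22 Q2W single-agent counts. Moving from 0/6 to 1/6 at 3/3 mg/kg takes P(over) from 0.013 to 0.054. Moving from 2/6 to 3/6 takes it from 0.157 to 0.339. One DLT crosses the limit only where the count is already high.

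**The case against.** The strongest reply is that the protocol already resolves the conflict and builds in checks. Section 6.2.3 points to the table. Section 6.2.3.1 says "All occurrences of DLT will be discussed and agreed at the dose decision teleconference", and Section 6.2.4 requires that Grade ≥2 "adverse events will be reviewed for all patients at the current dose level" before patients enter a higher dose. A patient without a DLT counts in the DDS only if sponsor and investigators agree that there was enough safety data to conclude that none occurred. This stands: classification by the table is the likely practice. But none of these safeguards says which of the two definitions is to be used.

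The second reply is that every Phase I event was judged under earlier versions of Tables 6-4 and 6-5. This also stands. Both the undercount and the DDS exclusion are hypothetical for the actual data, because it is not known whether the current Grade 2 rows and discontinuation rules were in force.

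Third, single-agent Phase II was not enrolled, so the Arm A estimate has limited downstream use. That is fair, although Arm A DLT data enter the Arm B model without down-weighting.

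It could also be said that the lead-in's closing clause misfits the first block, whose rows are exceptions. That is a weak point, since the block's header is itself a criterion.

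**Conclusion.** The contradiction is real and stands in the current text. A rule for the Phase I primary variable, the BLRM input and DDS entry gives a wrong count if followed literally. The grade ≥3 floor is the part to correct.

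A reader might infer that DLTs were miscounted, or that the MTD or RP2D is wrong. The documents do not support that. No misclassified event is shown, the versions that governed Phase I are not available, and the procedures favour the table reading.

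On size, one DLT can change an early escalation step (0.108 against 0.262 at 10 mg/kg). It does not bar 10 mg/kg on the accumulated Q2W data (0.032, at most 0.130). These figures rest on the Table 14-7 prior, full weight for Q2W data only, and the January 2016 counts. The final Arm A counts are not given; 119 patients had been enrolled there by May 2017. Nothing firm can be said about the final Arm B estimate.

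**What to change.** In the lead-in of Section 6.2.4, delete the grade ≥3 condition and keep the attribution and window conditions. Replace the closing clause about meeting criteria in Table 6-4 with: *and is classified as a DLT by Table 6-4, including all its exceptions (infusion reactions are not DLTs), its listed Grade 2 events and its case-by-case provisions.* Infusion reactions need naming because their exclusion sits in the second block of the table, outside the list of exceptions for Grade 3 and 4 events.

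Before the final analysis, check once that each patient's DLT and DDS status was assigned by the Table 6-4 version in force for that patient and not by the grade floor. Include patients stopped early for a listed Grade 2 event, and record the version used. Rerun the BLRM only if a count changes.

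The cost is one sentence and one data check. The rewording cannot alter completed Phase I decisions; the check is what protects the reported estimate.

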##### **DLT window:**

- Arm A and Arm C with single agent LAG525: 28 days (one cycle) (21 days for patients on Q3W dosing schedule).
- Arm B with combination of LAG525 and PDR001: 56 days (two cycles) (42 days for patients on Q3W dosing schedule).

Emerging data from the new field of immune-immune combination studies suggest that some immune-related adverse events have a prolonged latency ([Wolchok 2013](#)). As such, the DLT window for the combination arm in this trial is extended to the length of two cycles or 56 days.

National Cancer Institute Common Terminology Criteria for Adverse events (NCI CTCAE) version 4.03 will be used for all grading unless otherwise specified. For the purpose of dose-escalation decisions, DLTs will be considered and included in the BLRM.

The investigator must notify the Sponsor immediately of any unexpected CTCAE grade  $\geq 3$  adverse events or laboratory abnormalities. Prior to enrolling patients into a higher dose level, CTCAE grade  $\geq 2$  adverse events will be reviewed for all patients at the current dose level.

**Table 6-4 Criteria for defining dose-limiting toxicities**

During dose escalation, any Grade 3 or Grade 4 AEs related to study treatment occurring in cycle 1 (applies to dose escalation Arm A and Arm C) , and in cycles 1 and 2 (applies to dose escalation Arm B) are DLTs, EXCEPT:	
Fatigue	Grade 3 fatigue that resolves to $\leq$ Grade 1 within 7 days.
Fever, Infection	Grade 3 infection or fever, in the absence of neutropenia, that resolves within 7 days.
Hypertension	Grade 3 hypertension that resolves within 7 days after starting anti-hypertensive therapy.
Gastrointestinal	Grade 3 nausea and vomiting that resolves to $\leq$ Grade 1 within 48 hours of starting optimal anti-emetic therapy.
	Grade 3 diarrhea that resolves within 7 days after starting optimal anti-diarrhea treatment, where colitis is not suspected.
Hepatic	Grade 3 ALT or AST in the absence of significantly increased bilirubin that resolves to $\leq$ Grade 1 within 7 days.
Amylase and lipase	Asymptomatic Grade $\geq 3$ amylase or lipase.
Dermatologic	Grade 3 non bullous rash without epidermal detachment that resolves to $\leq$ Grade 1 within 7 days of starting treatment.
Hematologic	Grade 3 neutropenia without fever or other clinical symptoms that resolves to $\leq$ Grade 1 within 7 days.
	Grade 3 thrombocytopenia without clinically significant bleeding.
	Grade 3 anemia that resolves within 7 days in the absence of transfusion.
	Lymphopenia of any grade is not a DLT.
Electrolytes	Grade 3 electrolyte abnormalities that resolve to $\leq$ Grade 1 within 7 days after starting supplementation.
Musculoskeletal	Grade 3 asymptomatic increase in creatine kinase that resolves within 14 days in the absence of evidence of cardiac involvement.
Immune-related toxicities*	In general, a Grade 3 immune-related AE that resolves to $\leq$ Grade 1 within 7 days of starting appropriate treatment is not a DLT.

**The following Grade 2 AEs related to study treatment are considered DLTs:**

Ocular disorders	Grade 2 eye pain or reduction of visual acuity are DLTs if they do not respond to topical therapy and do not improve to Grade 1 severity within 2 weeks of the initiation of topical therapy, OR if they require systemic treatment.
Pneumonitis	Grade 2 pneumonitis is a DLT if it does not resolve to $\leq$ Grade 1 within 7 days of starting corticosteroids.
Myocarditis	Grade 2 myocarditis is a DLT.
Colitis	Grade 2 colitis is a DLT if it persists $>$ 7 days despite treatment with corticosteroids.
Hepatic	Grade 2 ALT or AST accompanied by bilirubin $>1.5$ x ULN is a DLT.
Dermatologic	Grade 2 bullous disease that does not resolve to $\leq$ Grade 1 within 7 days of starting corticosteroids is a DLT.
Other adverse events	Other clinically significant toxicities, including a single event or multiple occurrences of the same event that lead to a dosing delay of $>$ 7 days within the DLT window, may be considered to be DLTs by the Investigators and Novartis, even if not CTCAE grade 3 or higher. Infusion reactions will not be considered as dose limiting because they are idiosyncratic and not related to dose.

\* Depending on the nature of the AE, there may be cases where immune-related Grade 2-3 AEs of any duration warrant declaration of a DLT and permanent study discontinuation (e.g. Stevens-Johnson Syndrome (SJS)). DLT determination not already outlined in this table will be made on a case-by-case basis after Investigator discussion with the Novartis Medical Monitor.

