### Study status

As of 26-Mar-2019, 450 patients have been enrolled in this trial. Of the 450 patients, 255 patients have been treated in the dose escalation part, of which 134 received LAG525 single agent and 121 received LAG525 in combination with PDR001 and 235 patients that have been treated in the combination dose expansion part. As of 26-Mar-2019 there were 39 active patients. Ten of these patients were enrolled in the dose escalation part and 29 patients were enrolled in the dose expansion part.

[REDACTED]

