### Study status:

The CLAG525X2101C study started enrollment on 17-June-2015. As of 21-Jun-2018, 255 patients have been treated in the Phase I study part and 212 patients have been treated in the Phase II study part which is currently ongoing. As anti-tumoral activity was not observed with LAG525 single agent but was seen at several dose levels of LAG525 in combination with PDR001, it was decided that only the combination portion Phase II expansion would be enrolled. This was not a consequence of any safety concern.

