## Changes to the protocol

Changes to specific sections of the protocol are shown in the track changes version of the protocol using strike through red font for deletions and red underline for insertions.

Glossary of terms was updated to include the definition for Personal Data and Withdrawal of study consent.

Section 5.3 exclusion criteria was changed to align with updated recommended dose limiting toxicity table.

Section 6.2 and Table 6-4 was updated to align with recently published guidelines on the clinical management of suspected immune-related toxicities.

Section 6.3 and Table 6-5 was updated to align with recently published guidelines on the clinical management of suspected immune-related toxicities.

Section 6.3.5 was updated to include allowed dose of systemic steroid used for the management of other concurrent medical conditions.

Section 7.1.3 was updated to have progressive disease include per RECIST 1.1 or as determined clinically by the Investigator.

Section 7.1.4 was updated to differentiate sample use after a patient withdraws consent based on different regulations/laws around the world.

Table 7-6 footers were adjusted to clarify that the 1-hour post infusion sample should be taken at all dosing visits from Cycle 1 through Cycle 6 unless noted otherwise.

Section 8.3 was updated to note that if the mother consents outcome data will be collected for up to 12 months after the birth of the child.

Section 10.5.2 was updated to clarify data reporting for secondary efficacy objectives.

Section 10.5.3.1 was updated to clarify what analysis set will be used for safety analysis.

Section 10.5.3.2 was updated to clarify which adverse event summaries will be produced.

Section 14.2 was updated to clarify the selection of new measurable lesions and calculation of follow-up evaluations.

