### 5.3 Exclusion criteria

Patients eligible for this study must not meet **any** of the following criteria:

1. Presence of symptomatic central nervous system (CNS) metastases, or CNS metastases that require local CNS-directed therapy (such as radiotherapy or surgery), or increasing doses of corticosteroids within the prior 2 weeks. Patients with treated brain metastases should be neurologically stable for at least 4 weeks prior to study entry and off steroids for at least 2 weeks before administration of any study treatment.
2. History of severe hypersensitivity reactions to study treatment ingredients or other mAbs
3. Patient with out-of-range laboratory values defined as:
  - Creatinine clearance (calculated using Cockcroft-Gault formula, or measured)  $< 40$  mL/min
  - Total bilirubin  $> 1.5 \times$  ULN, except for patients with Gilbert's syndrome who are excluded if total bilirubin  $> 3.0 \times$  ULN or direct bilirubin  $> 1.5 \times$  ULN
  - Alanine aminotransferase (ALT)  $> 3 \times$  ULN
  - Aspartate aminotransferase (AST)  $> 3 \times$  ULN
  - Absolute neutrophil count (ANC)  $< 1.0 \times 10^9/L$
  - Platelet count  $< 75 \times 10^9/L$
  - Hemoglobin (Hgb)  $< 9$  g/dL
  - Potassium, magnesium, calcium or phosphate abnormality CTCAE  $>$  grade 2

4. Clinically significant cardiac disease or impaired cardiac function, including any of the following:
  - Clinically significant and/or uncontrolled heart disease such as congestive heart failure requiring treatment (NYHA grade  $\geq 2$ ), uncontrolled hypertension or clinically significant arrhythmia
  - QTcF  $>470$  msec on screening ECG or congenital long QT syndrome
  - Acute myocardial infarction or unstable angina pectoris  $< 3$  months prior to study entry
5. Active, known or suspected autoimmune disease. Patients with vitiligo, type I diabetes mellitus, residual hypothyroidism due to an autoimmune condition only requiring hormone replacement, psoriasis not requiring systemic treatment, or other conditions not expected to recur, are permitted to enroll. Patients previously exposed to anti-PD-1 / PD-L1 treatment who are adequately treated for skin rash or who are receiving replacement therapy for endocrinopathies should not be excluded.
6. Patients who required discontinuation of treatment due to treatment-related toxicities with prior therapy directed against the same target as the drug(s) under study in this protocol.

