## 6.3 Dose modifications

### 6.3.1 Dose modification and dose delay

For patients who do not tolerate the protocol-specified dosing schedule, dose or schedule adjustments are permitted in order to allow the patient to continue the study treatment. The following guidelines need to be applied:

- If a patient experiences an AE meeting the criteria for DLT as outlined in [Section 6.2.4](#) (including events occurring after cycle 1 for Arm A and C or including events occurring after cycle 2 for Arm B), treatment should be withheld at the onset of the AE. Following resolution of the toxicity to grade 1 or to the patient's baseline value, the patient may resume study treatment after discussion with Novartis. If the investigator considers it to be in the patient's best interest to resume therapy before the toxicity has resolved to grade 1 or to the patient's baseline value, this may be permitted on a case by case basis after discussion with Novartis.
- For clinical management of suspected immune-related events, reference to consensus management guidelines is recommended such as those provided in the National Comprehensive Cancer Network (NCCN) Guidelines for the Management of Immunotherapy-Related Toxicities (available at : [https://www.nccn.org/professionals/physician\\_gls/default.aspx#immunotherapy](https://www.nccn.org/professionals/physician_gls/default.aspx#immunotherapy)), the American Society for Clinical Oncology clinical practice guideline for Management of Immune-Related Adverse Events in Patients Treated With Immune Checkpoint

Inhibitor Therapy ([Brahmer 2018](#)) or the European Society for Medical Oncology (ESMO) Clinical Practice Guidelines for Management of Toxicities from Immunotherapy ([Haanen 2017](#)). Note that in general, study treatment should be interrupted for grade 3 and 4 toxicities and for a subset of lower grade toxicities.

- Consider early referral to specialists with expertise in the diagnosis and management of immune-related AEs to thoroughly investigate events of uncertain etiology.
- Events not included in the study protocol or the reference guidance documents should be managed per institutional preference.

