Grade 3	Hold study treatment. Upon resolution to Grade $\leq$ 1 or baseline (hypertension, QTc) or $<$ 30 msec difference from baseline (QTc) within $\leq$ 7 days, may resume study treatment without dose modification after discussion with the Novartis Medical Monitor. Baseline ECG refers to the ECG(s) collected at screening.
Grade 4	Discontinue study treatment.
Other cardiovascular disorders	
Grade 2 (except myocarditis)	Hold study treatment. Upon resolution to Grade $\leq$ 1 or baseline, may resume study treatment without dose modification after discussion with the Novartis Medical Monitor.
Grade 2 myocarditis, or Grade $\geq$ 3 other cardiac disorders related to study treatment	Discontinue study treatment.
Gastrointestinal	
Diarrhea/colitis*	
Grade 1	May continue study treatment without dose modification. Manage per institutional standard guidelines which should include anti-diarrheal treatment, consideration of corticosteroid therapy, and hydration.
Grade 2	Hold study treatment. GI consultation. Upon resolution to $\leq$ Grade 1 and tapering of steroid requirement to $\leq$ 10 mg prednisone per day, resume study treatment without dose modification after discussion with the Novartis Medical Monitor.

Worst toxicity CTCAEa grade	Recommended Dose Modification
Grade 3	Hold study treatment. GI consultation. Upon resolution to ≤ Grade 1 and tapering of steroid requirement to ≤ 10 mg prednisone per day, consider resuming study treatment after discussion with the Novartis Medical Monitor.
Grade 4	Discontinue study treatment.
AST and/or ALT elevation	
Grade 2 AST and/or ALT	Hold study treatment. Manage per institutional practice. Upon resolution to ≤ Grade 1 or baseline, consider resuming study treatment without dose modification.
Grade 2 transaminitis with bilirubin >1.5 x ULN (unless Gilbert's syndrome)	Discontinue study treatment.
Grade 3 AST and/or ALT	Hold study treatment. Manage per institutional practices. Upon resolution to ≤ Grade 1 or baseline within 7 days, consider resuming study treatment without dose modification after discussion with the Novartis Medical Monitor. Otherwise, discontinue study treatment.
Grade 4 AST and/or ALT	Discontinue study treatment.
Isolated total bilirubin elevation**	
Grade 2	Hold study treatment. Upon resolution to ≤ Grade 1 or baseline, may continue study treatment without dose modification.

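### Minor: Table 6-4's Grade 2 hepatic DLT row has no Gilbert's qualifier, so an eligible Gilbert's patient with a related Grade 2 ALT/AST rise and unchanged bilirubin counts as a DLT

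*Protocol*

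**What the plan says.** Three parts of the current protocol deal with the same laboratory picture.

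- **Section 5.3, exclusion criterion 3.** Total bilirubin above 1.5 x ULN excludes a patient, "except for patients with Gilbert's syndrome who are excluded if total bilirubin" is above 3.0 x ULN or direct bilirubin is above 1.5 x ULN.
- **Section 6.2.4, Table 6-4, Grade 2 block, hepatic row.** "Grade 2 ALT or AST accompanied by bilirubin" above 1.5 x ULN is a DLT when related to study treatment. Gilbert's syndrome is not mentioned.
- **Section 6.3.1, Table 6-5.** The matching row, "Grade 2 transaminitis with bilirubin >1.5 x ULN (unless Gilbert's syndrome", calls for discontinuation. Grade 2 ALT/AST without that bilirubin condition is a hold: "Manage per institutional practice. Upon resolution to ≤ Grade 1 or baseline, consider resuming study treatment without dose modification".

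Table 6-4 has two uses. Its DLTs feed the Bayesian logistic regression model (BLRM), which SAP 2.6.1 runs on the dose-determining set. Section 6.3.1 also uses the DLT criteria as a trigger to withhold treatment, "including events occurring after cycle 1 for Arm A and C or including events occurring after cycle 2 for Arm B".

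On timing, Amendment 09 (16-Aug-2018) records that "Section 6.2 and Table 6-4 was updated to align with recently published guidelines on the clinical management of suspected immune-related toxicities". Its status paragraph, as of 21-Jun-2018, says "255 patients have been treated in the Phase I study part". Amendment 10 gives the same escalation total and adds: "As of 26-Mar-2019 there were 39 active patients".

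**The concern.** The hepatic row pairs a transaminase rise with raised bilirubin because together they suggest real liver injury. In Gilbert's syndrome the raised bilirubin is constitutional and unconjugated, and the protocol allows for this at entry and in Table 6-5. Table 6-4 does not, so for these patients the rule reduces to a Grade 2 ALT/AST rise alone, which in other patients does not meet the row.

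A DLT of that kind would enter the model at full weight. During escalation it could have held back a dose in a cohort of three or four. After escalation it could remain in the DLT summary and the final model fit.

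**Working it through.** **Reading the rows together.** Take a Gilbert's patient with baseline total bilirubin 2.0 x ULN, direct bilirubin at most 1.5 x ULN and ALT/AST at most 3 x ULN. After dosing, ALT rises to Grade 2 (above 3.0 to 6.0 x ULN, SAP Table 4-3), judged drug-related, with bilirubin unchanged.

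| Text | Condition | Result |
|---|---|---|
| Criterion 3 | total ≤3.0, direct ≤1.5 x ULN | eligible |
| Table 6-4 hepatic row | related Grade 2 ALT, bilirubin >1.5 x ULN | DLT |
| Table 6-5 matching row | same, unless Gilbert's | no discontinuation |
| Table 6-5 Grade 2 ALT/AST row | Grade 2 ALT | hold, may resume |

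**Looking for an exception elsewhere.**
- The relatedness wording (Section 6.2.4 and the block header) applies to the adverse event, which here is the transaminase rise. The row does not require the bilirubin to be related, raised from baseline or conjugated.
- The Table 6-4 footnote reserves case-by-case decisions for events the table does not already outline. This one is outlined.
- The dose decision teleconference (Section 6.2.3.1) agrees every DLT but states no exception.
- The lead-in to Section 6.2.4 speaks of grade 3 or higher, but the table expressly lists Grade 2 events.

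**What one such DLT does to the model.** The model is logit π(d) = log α + β log(d/3), with priors from Table 14-7 (Arm A) and Table 14-24 (Arm C). P(over) = P(π(d) ≥ 0.33 given the data), and a dose is eligible if this is below 0.25. It was evaluated on a 1001 x 1001 grid over (log α, log β).

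*Check against the plan.* Table 14-11 scenarios 1, 2, 4 and 5 publish 0.026, 0.108, 0.108 and 0.055; the grid gives 0.026, 0.110, 0.108 and 0.055. Scenario 8 publishes 0.193 and the grid gives 0.185. Table 14-26 scenarios 1, 2 and 16 publish 0.080, 0.111 and 0.033; the grid gives 0.081, 0.109 and 0.030. Agreement is therefore within about 0.01.

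*Arm A, small cohort.* After 0/4 at 1 mg/kg, P(over) at 10 mg/kg is:

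| At 3 mg/kg | 0/3 | 1/3 | 1/4 | 1/5 | 1/6 |
|---|---|---|---|---|---|
| P(over) | 0.108 | **0.262** | 0.230 | 0.205 | 0.185 |

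Only 1/3 exceeds 0.25, by 0.262 − 0.25 = 0.012, which is close to the numerical tolerance. The plan's own table points the same way: scenario 4 (0/3) moves to 10 mg/kg and scenario 5 (1/3) stays at 3 mg/kg.

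*Arm C, first cohort.* With one DLT among n = 3, 4, 5, 6 at 1 mg/kg, P(over) at 3 mg/kg is about 0.37, 0.29, 0.24 and 0.20. It crosses the limit for n = 3 and 4.

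*Larger data.* Table 14-22 is a 22-Jan-2016 cut with 12+11+4+4+5+3+4 = 43 evaluable Arm A patients, against 119 enrolled in Arm A by 31-May-2017 (Amendment 08). Q4W rows enter at their listed Q2W equivalents, unweighted.

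| Table 14-22 | P(over) 10 mg/kg | P(over) 15 mg/kg | Q2W rows only, 10 mg/kg |
|---|---|---|---|
| as given | 0.014 | 0.041 | 0.032 |
| 5 mg/kg: 2/4 to 1/4 | 0.004 | 0.016 | 0.010 |
| 1 mg/kg: 1/12 to 0/12 | 0.033 | 0.090 | 0.050 |

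The table has no 15 mg/kg row, so that column is extrapolation. Removing the 1 mg/kg DLT raises the high-dose figure because it steepens the fitted curve.

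For Arm C (14 patients, dose split not given), six assumed splits over 1/3/10 mg/kg give P(over) at 10 mg/kg of 0.004 to 0.028 with no DLT and at most 0.168 with one. Nothing in these larger data crosses 0.25. Arm B was not refitted, because its DLT counts are not in the documents.

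**Timing.** Counting 21-Jun-2018 as day 1, day 56 (the longest DLT window) is 15-Aug-2018, one day before Amendment 09.

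**The case against.** The strongest reply is that nothing can now turn on this. Escalation accrual stood at 254 by 31-May-2017 and at 255 by 21-Jun-2018. Even a patient first dosed on that last date would have finished the DLT window before Amendment 09 revised Table 6-4, and the earlier row is not shown. The present wording therefore cannot be shown to have classified any escalation DLT. That stands.

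For the patients still on study, Table 6-5 already holds treatment for any Grade 2 ALT/AST. Section 6.3.1 allows resumption once the toxicity returns to grade 1 or the patient's baseline, so a constitutional bilirubin is no bar. The only practical difference is that resuming needs discussion with the sponsor. That also stands.

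It can be added that DLT rules and dose-modification rules serve different purposes, and that over-counting DLTs is conservative. This explains the minor rating but does not justify the row: the protocol recognises Gilbert's syndrome at entry and in the matching management row, and gives no reason for omitting it here.

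A reader might infer that past DLT calls or a recommended dose were distorted. The documents do not support that: they identify no Gilbert's patient and do not show the row in force during escalation. A reader might equally infer from the refits that no dose could have been affected. They do not support that either: the Arm A data are an interim snapshot of 43 patients, the Arm C splits are assumed, and Arm B, the only arm taken into Phase II, is not covered.

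**Conclusion.** The row is wrong as written, and the point is minor. The text comparison is firm and needs no assumption beyond an eligible Gilbert's patient with total bilirubin above 1.5 and up to 3.0 x ULN who has a related Grade 2 ALT/AST rise. How many such patients there were cannot be computed from the documents.

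The error is toward caution. It could have changed a dose decision only in a very small early cohort, and then narrowly in Arm A. What remains live is the final DLT summary and model fit, if the row predates Amendment 09 and an affected patient exists, and the withholding trigger for the 39 patients active on 26-Mar-2019.

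**What to change.** 1. **Table 6-4.** Keep the Grade 2 hepatic row, but for patients with Gilbert's syndrome make the bilirubin condition direct bilirubin above 1.5 x ULN. A blanket exemption would miss a true conjugated rise. Criterion 3 already excludes Gilbert's patients above that direct-bilirubin limit, so none enters with the condition met.
2. **Table 6-5.** Replace the blanket Gilbert's exemption in the matching row with the same direct-bilirubin condition. Otherwise a Gilbert's patient with a conjugated rise would have a DLT yet be exempt from the discontinuation row.
3. **SAP 2.6.1.** Flag any hepatic DLT in a patient with baseline total bilirubin above 1.5 x ULN. Only if one exists, refit the BLRM with it recoded as a sensitivity analysis.

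Cost: items 1 and 2 need a written amendment with ethics approval (Section 12.1), so they should go with the next amendment rather than prompt one. Item 3 needs a SAP amendment, or an addendum after database lock (SAP Section 1). No new data are needed: Table 7-4 already requires direct bilirubin when total bilirubin exceeds Grade 1, which is above 1.5 x ULN in SAP Table 4-3.
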